18. CONFIDENTIALITY

Confidentiality of information is provided as a separate agreement.

19. FINANCING AND INSURANCE

Financing and insurance information is provided as a separate agreement.

20. PUBLICATION POLICY

The publication policy is provided as a separate agreement.

- follow a reasonable temporal sequence following the time of administration of the dose of study drug or study procedure or background treatment, etc.
- resolve or improve after discontinuation of study drug or study procedure or background treatment, etc.
- reappear or worsen when dosing with study drug or study procedure or background treatment, etc is resumed
- are known or suspected to be a response to the study drug or study procedure or background treatment, etc, based upon preclinical data or prior clinical data

NOTE: This list is not exhaustive.

1. OVERVIEW

The purpose of the statistical analysis plan (SAP) is to ensure the credibility of the study results by pre-specifying prior to the database lock the statistical approaches for the analysis of study data. The SAP is intended to be a comprehensive and detailed description of the strategy and statistical methods to be used in the analysis of data collected in the R1500-CL-1629 study. The content of this SAP is inclusive of both the first and second step analyses as described in the protocol.

This plan may be revised during the study to accommodate protocol amendments and adapt to unexpected issues in study execution that may affect planned analyses. These revisions will be based on blinded data review, and a final plan will be issued prior to the first step database lock (i.e. before treatment assignments become known). For the purposes of this document, REGN1500 will be referred to as “evinacumab”.

1.1. Background/Rationale

Homozygous familial hypercholesterolemia (HoFH) is a rare and serious genetic condition resulting in severely elevated low-density lipoprotein cholesterol (LDL-C) and accelerated cardiovascular disease (CVD). Familial hypercholesterolemia results from mutations in the low-density lipoprotein receptor (LDLR), or in 3 associated genes: proprotein convertase subtilisin/kexin type 9 (PCSK9), apolipoprotein B (Apo B), and LDLR adaptor protein 1 (LDLRAP1).

Homozygous FH is frequently caused by mutations in both alleles of the LDLR gene and results in the decreased clearance of LDL particles from plasma. Patients with HoFH have severe hypercholesterolemia which can lead to an exceedingly high risk of developing premature atherosclerosis, as well as valvular and supra-valvular stenosis. In children as young as 7 years of age, mild coronary atherosclerosis can be evident even without any clinically apparent coronary artery disease. This accelerated atherosclerosis results in premature CVD and an increased risk of a cardiovascular (CV) event.

Angiotensin-like 3 (ANGPTL3) has recently emerged as a potential target for the treatment of elevated levels of triglycerides (TGs) and for the treatment of elevated levels of LDL-C, both risk factors for the development of CVD. ANGPTL3 acts as a natural inhibitor of lipoprotein lipase, an endothelial-bound enzyme involved in the hydrolysis of the TG content of very-low-density lipoproteins and chylomicron lipoproteins. Patients who are homozygous for loss-of-function (LOF) mutations in ANGPTL3 have lower levels of LDL-C (mean difference of 48% versus control family members).

Evinacumab (REGN1500) is a fully human mAb, created with Regeneron’s VelocImmune technology platform, which specifically binds to ANGPTL3. Additional background information on the study drug and development program can be found in the Investigator’s Brochure.

1.2. Study Objectives

1.2.1. Primary Objectives

The primary objective of the study is to demonstrate the reduction of LDL-C by evinacumab 15 mg/kg intravenously (IV) in comparison to placebo after 24 weeks in patients with HoFH.

1.2.2. Secondary Objectives

The secondary objectives of the study are:

- To evaluate the effect of evinacumab 15 mg/kg IV on other lipid parameters (i.e., apolipoprotein [Apo B], non-high-density lipoprotein cholesterol [non-HDL-C, total cholesterol [TC]) in patients with HoFH)
- To evaluate the effect of evinacumab on LDL-C goal attainment
- To assess the effect of evinacumab on patients meeting eligibility criteria for apheresis (using German and US apheresis criteria)
- To evaluate the safety and tolerability of evinacumab 15 mg/kg IV in patients with HoFH
- To determine concentrations of evinacumab in patients with HoFH
- To evaluate the potential development of anti-evinacumab antibodies

1.2.3. Other Objectives

- Genotyping will be performed for all patients to identify mutations causing HoFH and to explore potential differences in efficacy and safety based on type of LDLR function variant.
- To assess the effect of evinacumab on quality of life using the EQ-5D and HADS QOL questionnaires.

1.2.4. Modifications from the Statistical Section in the Final Protocol

The summary of modifications is listed in the following table.

Item	Protocol Section	Description
1	10.3.2.1 Double-Blind Safety Analysis Set	
SAP Section 3.2:
 
The second item for determining the as-treated treatment group will be changed from
 
“For patients receiving study drug from more than 1 treatment group during the trial, the treatment group allocation for as-treated analysis will be the one in which the patient was treated with the highest number of infusions.”
 
to
 
For patients receiving study drug from more than 1 treatment group during the trial, the treatment group allocation for as-treated analysis will be evinacumab.

1.2.5. Revision History for Statistical Analysis Plan Amendments

This is the first version of Statistical Analysis Plan (SAP).

2. INVESTIGATION PLAN

2.1. Study Design and Randomization

This is a randomized, double-blind, placebo-controlled, parallel-group study to evaluate the efficacy and safety of evinacumab in patients with homozygous familial hypercholesterolemia (HoFH).

Patients who meet all the inclusion criteria and none of the exclusion criteria will be randomized in a 2:1 ratio to receive evinacumab 15 mg/kg IV every 4 weeks (Q4W) or matching placebo IV Q4W for the 24-week double-blind treatment period (DBTP). The randomization will be stratified by apheresis treatment (Yes, No) and by region (Japan, Rest of World). After completion of the DBTP, all patients will enter a 24-week open-label treatment period (OLTP) and receive open-label evinacumab 15 mg/kg IV Q4W.

After completion of the 24-week OLTP, all patients who have successfully completed this study may have the opportunity to participate in a separate open-label (OL) study. All patients that enroll in the separate OL study will continue to receive open-label evinacumab at a dose of 15 mg/kg IV Q4W. Those patients who do not participate in the separate open-label study will undergo a 24-week follow-up after the last dose of study treatment.

The analyses will be conducted in 2 steps. The first analysis will be conducted as soon as all patients have been randomized and all data through week 24 (double-blind treatment period) has been collected and validated; this first analysis will consist of the final analysis of the double-blind primary and secondary efficacy endpoints. The safety analysis will be performed on all safety data collected and validated at the time of the first step analysis database lock. Since the double-blind primary efficacy measure data collection will have been concluded at the time of this first analysis, the significance level for the study remains at 0.05.

The second analysis will be performed with the data from the open-label treatment period and will consist of the final analysis for the safety and efficacy measures beyond week 24-time point.

The results of the first analysis will not be used to change the conduct of the ongoing study in any aspect. Individuals involved in the first step analysis of the study will not be involved in the conduct of the study afterwards; individual patient identification will not be released to anyone who is directly involved in the conduct of the study. The first step analysis process, the measures used to protect the blind and the integrity of the study, the communication plan, and the confidentiality agreement will be described in a separate document.

2.2. Sample Size and Power Considerations

For the primary efficacy hypothesis during the DBTP, a total sample size of 57 patients (38 on evinacumab and 19 on placebo) will have 90% power based on a two sample t-test to detect a treatment group difference in mean percent change LDL-C of 38% with a 0.05 two-sided significance level and assuming a common standard deviation of 35% using nQuery 7.0. This

sample size has been adjusted for a 5% non-evaluable patient rate for the primary efficacy endpoint, and a 15% dropout rate.

To gain experience with evinacumab in the population of Japanese patients, this study will plan to enroll up to 9 patients in Japan. Due to the rare patient population planned for evaluation, the sample size of 9 patients (15% of the planned study sample size) was chosen for practical reasons, centered on the feasibility to identify and enroll these patients into the trial. Based on the Ministry of Health, Labor, and Welfare 2007 “Basic Principles on Global Clinical Trials” method 1, a sample size of 12 (21%) will be needed to achieve 80% probability that the effect in Japan is at least ½ of the global effect. A sample size of 9 provides approximately 77% probability.

2.3. Study Plan

This study consists of the following periods: up to an 8-week run-in period (for patients who may require HoFH genotyping, for patients whose background medical lipid modifying therapy (LMT) has not been stable prior to screening or whose apheresis settings and/or schedule have not been stable for at least 8 weeks prior to screening), a 2-week screening period, a 24-week double-blind treatment period (DBTP), and a 24-week open-label treatment period (OLTP), and a 24-week follow-up period after the last dose of study drug for those patients who choose not to enter the open-label study (See [Figure 1.](#))

The Study event table is presented in [Appendix 10.9](#).

Figure 1: Study Flow Diagram

Run-in ¹	Screening	Double-Blind Treatment ²	Open-Label Treatment ³	Follow-up ⁴
V1a Day -70	V1 Day -14	V2 Day 1 Baseline	V3 to V9 Wk 2 to 24	End of DBTP ³
			V10 to V15 Wk 28 to 48	End of OLTP
				V16 to V20 Wk 52 to 68 EOS

¹ Patients who are undergoing apheresis therapy with a schedule and/or apheresis settings that have not been stable for at least 8 weeks before the screening visit will enter a run-in period before the screening period. Patients who are on background LMT that has not been stable for at least 4 weeks (6 weeks for fibrates, 8 weeks for PCSK9 inhibitor antibodies) before the screening visit will enter the run-in period to stabilize their LMT before entering the screening period. Patients who have completed the R727-CL-1628 study and meet all the eligibility criteria for this study can be enrolled directly. The end of the open-label treatment visit from the R727-CL-1628 study can serve as the baseline/day 1 visit for this study.

² Patients will receive study drug IV Q4W starting at day 1.

³ The open-label treatment period begins at week 24 (day 169) when all patients will receive evinacumab 15 mg/kg IV Q4W. The last dose of evinacumab will be at week 44.

⁴ Follow-up only for patients who do not enter a separate, optional OL study, R1500-CL-1719 or prematurely discontinue study treatment in this study.

3. ANALYSIS POPULATIONS

In accordance with guidance from the International Conference of Harmonization of Technical Requirements for Registration of Pharmaceuticals for Human Use (ICH) guideline ICH E9 Statistical Principles for Clinical Trials (ICH, 1998), below are the patient populations defined for statistical analysis. Two efficacy populations are planned for this study, specifically the Intent-to-Treat (ITT) population and the Modified Intent-to-Treat population (mITT). The primary efficacy analysis population is the ITT population. Additional patient populations are defined for safety, anti-drug (evinacumab) anti-body (ADA), pharmacokinetic (PK), quality-of-life, and open-label analyses. For the purposes of the definitions below, a patient is considered randomized to study treatment when they have been screened and received a double-blind treatment kit number allocated and recorded in the IVRS/IWRS database, regardless of whether the treatment kit was used or not.

As with all trials, odd cases (usually rare) occur for patient eligibility in the analysis populations. The following are three cases with the planned resolution of each type of case should they occur.

- Patients administered study treatment without randomization or before randomization will not be considered as “randomized” and therefore will not be included in any analysis population. The safety experience from these patients will be reported separately.
- For patients found to be randomized more than once in this trial, safety data from the first randomization will be included in the safety population, with safety data associated with the later randomization reported separately. Inclusion of efficacy data from the patient randomized more than once in the two efficacy populations will be decided on a case-by-case basis prior to the unblinding of treatment assignments and documented in the study report.
- Patients successfully randomized and administered study treatment, but later found to violate inclusion/exclusion criteria, will be included in all analyses with appropriate documentation for the protocol deviation.

3.1. Efficacy Analysis Sets

3.1.1. Intent-to-Treat (ITT)

The ITT population is defined as all randomized patients who received at least one dose or part of a dose of double-blind study drug. Patients in the ITT population will be analyzed according to the treatment group allocated by randomization (i.e., as randomized patient group).

3.1.2. Modified Intent-to-Treat (mITT)

The modified ITT (mITT) population is defined as the all randomized population who took at least 1 dose or part of a dose of study drug and have an evaluable primary endpoint. The endpoint is considered as evaluable when both of the following conditions are met:

- Availability of at least 1 measurement value for calculated LDL-C before first dose of study drug (i.e., baseline).
- Availability of at least 1 calculated LDL-C value during the efficacy treatment period and within one of the efficacy analysis windows in the DBTP up to week 24. The efficacy treatment period is defined as the time from the first double-blind study drug administration up to 35 days after the last double-blind study drug administration, or up to the first dose of the open-label study drug, whichever is earlier.

Patients in the mITT population will be analyzed according to the treatment group allocated by randomization.

3.2. Double-Blind Safety Analysis Set

The double-blind safety analysis set (SAF) considered for safety analyses will be the randomized population who received at least 1 dose or part of a dose of double-blind study drug. Patients will be analyzed according to the treatment received (placebo or evinacumab). In addition:

- Randomized patients for whom it is unclear whether they took the study drug will be included in the safety population as randomized.
- For patients receiving study drug from more than 1 treatment group during the trial, the treatment group allocation for as-treated analysis will be evinacumab.

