10.3.2. Safety Analysis Sets

10.3.2.1. Double-Blind Safety Analysis Set

The double-blind safety analysis set (SAF) considered for safety analyses will be the randomized population who received at least 1 dose or part of a dose of double-blind study drug. Patients will be analyzed according to the treatment received (placebo or evinacumab). In addition:

- Randomized patients for whom it is unclear whether they took the study drug will be included in the safety population as randomized.
- For patients receiving study drug from more than 1 treatment group during the trial, the treatment group allocation for as-treated analysis will be the one in which the patient was treated with the highest number of infusions.

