3.3. Open-Label Safety Analysis Set

The open-label SAF considered for safety analyses will be the randomized population who received at least 1 dose or part of a dose of open-label study drug.

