4.8.1. Adverse Events Variables

The period of safety observation starts from the time when the patient gives informed consent and continues into the following periods:

- The PRE-TREATMENT period is defined from the day the ICF is signed to the day before the first dose of double-blind study treatment administration.
- The double-blind treatment-emergent adverse event (TEAE) period is defined from the day of the first dose of double-blind study treatment administration to the day of the last dose of double-blind study treatment administration + 168 days (24 weeks) for those patients not proceeding into the OLTP, or up to the day before the first dose of open-label study treatment administration for those patients proceeding into the OLTP

The double-blind TEAE period will include:

- The TREATMENT period is defined from the day of first double-blind study treatment administration up to the day of last double-blind study treatment administration + 35 days. For patients entering into the OLTP, the treatment period will be truncated at the day before the first dose of open-label study treatment administration.
- The RESIDUAL TREATMENT period is defined from the day of last double-blind study treatment administration + 36 days up to the day of last double-blind study treatment administration + 168 days (24 weeks), or up to the day before first dose of open label study treatment administration, whichever is earlier.
- The open-label treatment-emergent adverse event (TEAE) period is defined from the day of the first open-label study treatment administration to the day of the last open-label study treatment administration + 168 days (24 weeks). For patients entering the open-label study R1500-CL-1719, the TEAE period will be truncated at the day before first study treatment administration in R1500-CL-1719.

The open-label TEAE period will include:

- The TREATMENT period is defined from the day of first open-label study treatment administration up to the day of last open-label study treatment administration + 35 days.
- The RESIDUAL TREATMENT period is defined from the day of last open-label study treatment administration + 36 days up to the day of last open-label study treatment administration + 168 days (24 weeks).

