5.8. Analysis of Safety Data

The summary of safety results will be presented separately for the DBTP and OLTP, unless otherwise noted. Safety summaries for the DBTP will be presented by treatment groups (evinacumab, placebo) containing patients from the double-blind safety analysis set. Safety summaries for the OLTP will be presented by all patients and by treatment group in DBTP (i.e.,

evinacumab, placebo), for patients in the open-label safety analysis set. No formal inferential testing will be performed for either period. Summaries will be descriptive in nature.

General common rules

All safety analyses will be performed, unless otherwise specified, using the following common rules:

- Safety data in patients who do not belong to the safety analysis set (i.e., exposed but not randomized) will be listed separately.
- PCSV values are defined as abnormal values considered medically important by the Sponsor according to predefined criteria/thresholds based on literature review and defined by the Sponsor for clinical laboratory tests and vital signs (PCSV version dated January 2009 [Appendix 10.4]). Considering that the threshold defined in the PCSV list for monocytes and basophils can be below the ULN, the following PCSV criterion will be used for the PCSV analysis of monocytes and basophils:
 - PCSV criterion for monocytes: >0.7 Giga/L or $>ULN$ (if $ULN \geq 0.7$ Giga/L).
 - PCSV criterion for basophils: >0.1 Giga/L or $>ULN$ (if $ULN \geq 0.1$ Giga/L).
- PCSV criteria will determine which patients had at least 1 PCSV during the respective TEAE periods, taking into account all evaluations including unscheduled or repeated evaluations.
- The treatment-emergent PCSV denominator by treatment group for a given parameter will be based on the number of patients assessed for that given parameter at least once during the respective TEAE periods.
- All measurements, scheduled or unscheduled, fasting or not fasting, will be assigned to Global Analysis Windows defined in Appendix 10.2 /Table 1 in order to provide an assessment for the screening visit through follow-up visit time points.
- For quantitative safety parameters including central laboratory measurements and vital sign scores, descriptive statistics will be used to summarize observed values and change from baseline values by visit.

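### The as-treated rule for the double-blind safety set covers the whole trial rather than the double-blind period, so read literally it moves placebo patients to evinacumab once they receive an open-label dose

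*SAP*

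**What the plan says.** SAP 3.2 defines the double-blind safety set as randomized patients given any double-blind study drug, grouped by treatment received. It then settles mixed exposure: "For patients receiving study drug from more than 1 treatment group during the trial, the treatment group allocation for as-treated analysis will be evinacumab". SAP 1.2.4 lists this sentence as a deliberate change from Protocol 10.3.2.1, which assigned such a patient to "the one in which the patient was treated with the highest number of infusions". Both rules apply to exposure *during the trial*.

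The trial does not end with the double-blind period. SAP 2.1 states: "After completion of the DBTP, all patients will enter a 24-week open-label treatment period (OLTP) and receive open-label evinacumab 15 mg/kg IV Q4W". SAP 3.3 treats the product given in that period as study drug, since it defines the open-label set by patients who "received at least 1 dose or part of a dose of open-label study drug".

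Two other sections bear on intent. SAP 4.8.1 ends the double-blind adverse event period "up to the day before the first dose of open-label study treatment administration for those patients proceeding into the OLTP". SAP 5.8 says: "Safety summaries for the OLTP will be presented by all patients and by treatment group in DBTP".

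**The concern.** A placebo patient who completes the double-blind period and receives one open-label infusion has had both placebo and evinacumab as study drug within the trial. On the plain words of SAP 3.2, that patient belongs in the evinacumab column of the double-blind safety tables. Only exposure before open label is relevant to those tables, and the rule does not say so.

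If the rule were programmed as written, events that occurred on placebo would be counted under evinacumab, and AE denominators would shift with them, because SAP 5.8.1 takes percentages over the safety set within each treatment group. The adverse event cut-off in SAP 4.8.1 does not repair this. It decides which events count as double-blind events, not which column the patient is in.

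**Working it through.** **Inputs.** SAP 2.2 plans 57 patients, 38 on evinacumab and 19 on placebo. This agrees with the 2:1 ratio in SAP 2.1: 57 × 2/3 = 38 and 57 × 1/3 = 19. The documents give no figure for the share *d* of placebo patients who never receive an open-label dose, so it is varied as an assumption. The 15% row borrows the dropout rate in SAP 2.2, which was set for the sample size and not for this purpose.

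**Step 1: the literal rule.** Placebo patients moved = 19 × (1 − d), rounded. Placebo left = 19 − moved. Evinacumab column = 38 + moved.

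| d (assumed) | Moved | Evinacumab | Placebo |
|---|---|---|---|
| 0% | 19 | 57 | 0 |
| 5% | 18.05 → 18 | 56 | 1 |
| 15% | 16.15 → 16 | 54 | 3 |
| 20% | 15.2 → 15 | 53 | 4 |
| 30% | 13.3 → 13 | 51 | 6 |

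**Step 2: what the SAP's change does.** Double-blind infusions fall at weeks 0, 4, 8, 12, 16 and 20, and open-label infusions at weeks 24, 28, 32, 36, 40 and 44. Under the protocol's majority rule, a placebo patient with all 12 infusions has 6 of each, a tie. A patient with fewer open-label than placebo infusions stays in placebo. Under the SAP rule a single open-label infusion is enough to move the patient. The scope wording comes from the protocol, but the SAP's automatic assignment gives it much more force.

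**Step 3: when it would bite.** SAP 7 sets the first-step safety cut-off at the date of the last week 24 visit, and open-label dosing starts at week 24. By then nearly all placebo completers will have had an open-label dose, so the first-step tables would already be affected.

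**Step 4: direction of the distortion.** As an illustration only, assume an event rate of 30% on evinacumab and 10% on placebo, with 16 patients moved. The evinacumab column would show (38 × 0.30 + 16 × 0.10) / 54 = 13.0 / 54 = 24.1% instead of 30%. A real difference would be diluted, and the comparison would rest on 3 placebo patients.

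**Step 5: with the rule limited to the double-blind period.** The split stays at 38/19, apart from patients who really received both treatments before open label.

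**The case against.** The strongest reply is that context already limits the rule. It is a sub-point of a set defined by double-blind study drug. SAP 3.1.2 uses unqualified *study drug* for the double-blind product when it defines baseline, and adds *open-label* when it means the other. *Treatment group* elsewhere in the SAP usually means the double-blind arm. On that reading, a patient with drug from more than one group is a dispensing error, and the planned move to open label is a change of period, not of group.

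Much of this stands as evidence of intent. A reader might infer that the double-blind safety comparison will lose its control arm, or that the sponsor means to pool the arms. The documents do not support either. SAP 5.8 requires double-blind safety tables by evinacumab and placebo and splits open-label summaries the same way. SAP 5.7.2.5 forms open-label subgroups by treatment received in the double-blind period. These provisions make sense only if placebo patients keep their group, and a careful programmer would probably read the rule that way. Nor can a reader infer any effect on efficacy: SAP 3.1.1 and 3.1.2 analyse the ITT and mITT sets as randomized.

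The reply does not make the wording right. The SAP is not consistent about *study drug*: SAP 2.3 counts follow-up from the last dose of study drug, which for a patient completing open label is an open-label dose. SAP 3.4, 3.5 and 3.6 expressly tie treatment assignment to the double-blind period, and SAP 3.2 does not. It is also fair to say that the number of patients moved is not known in advance. Patients who stop study drug are asked to remain in the double-blind period (Protocol 7.4.2), so the 15% dropout rate need not equal the share who miss open label.

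**Conclusion.** The point holds as a scope error in a stated rule. Taken literally, SAP 3.2 and the SAP 1.2.4 table move to evinacumab, in the double-blind safety set, every placebo patient with at least one open-label dose: 19 of 19 if all enter open label, 16 if 15% do not, 13 if 30% do not. The counts rest on the planned arm sizes and on assumed shares. Placebo patients who never receive open-label drug are not touched.

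The rest of the SAP shows that the literal result is not what is meant, so the practical risk is misprogramming or a query at review, not a planned loss of the comparison. The exposure is confined to tables built on the double-blind safety set. The primary and key secondary efficacy analyses and the sample size do not change. This is a minor point that is worth correcting because the rule is listed as a deliberate modification and should be safe to program as written.

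**What to change.** In SAP 3.2, and in the replacement text of the SAP 1.2.4 table, change *during the trial* to *during the double-blind treatment period (before the first open-label dose)*. The part of that table that reproduces the protocol's sentence can stay as it is.

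The rule then covers only patients who received both treatments within the double-blind period, for example through a dispensing error. They still go to evinacumab, so the change that SAP 1.2.4 set out to make is kept. The cost is a few words before the first-step database lock, with no new data, no new analysis and no effect on the sample size.
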